3.1 Primary Endpoint

1. Ventilator-Free Days to study day 28

VFDs is a composite endpoint that is affected by mortality and duration of mechanical ventilation in survivors (Schoenfeld, 2002), which has been chosen as the primary endpoint for a number of reasons. VFDs provide a validated measure of improved lung function, even if overall mortality is only minimally altered. In addition to also possibly altering inflammation, full-calorie feedings may place patients at risk for aspiration, which may result in increased mortality, but will result in fewer ventilator-free days, even in non-fatal cases. Further, VFDs is a measure of a morbidity outcome and it is directly related to "days of assisted ventilation." However, a trend in one treatment group toward early patient death would likely decrease the number of days of assisted ventilation. This example of decreased days of assisted ventilation is misleading as the treatment group actually had a worse outcome. Measuring ventilator days in survivors would offset the problem of early mortality decreasing ventilator days. However, if a treatment group had a favorable trend towards improved survival, but required additional ventilator days for survival, "average number of ventilator days in survivors" could also be misleading. VFDs represent a measurable outcome that is favorably affected by both shorter duration of assisted ventilation in survivors and lower mortality.

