VFD to day 28 is defined as the number of days from the time of initiating unassisted breathing to day 28 after randomization, assuming survival for at least two consecutive calendar days after initiating unassisted breathing and remains free of assisted breathing to day 28. If a patient returns to assisted breathing and subsequently achieves unassisted breathing to day 28, VFD will be counted from the end of the last period of assisted breathing to day 28 unless a period of assisted breathing was less than 24 hours and the purpose of assisted breathing was a surgical procedure. If a patient was receiving assisted breathing at day 27 or dies prior to day 28, VFD will be zero. Patients transferred to another hospital or other health care facility prior to day 28 while still receiving assisted breathing will be followed to assess this efficacy measure. Unassisted breathing is defined as breathing with facemask or nasal prong oxygen (or room air) following extubation, T-tube breathing, breathing with continuous positive airway pressure (CPAP \leq 5 cm H₂O without PS or IMV assistance), or tracheotomy mask breathing.

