3.2 Secondary Endpoints

1. The secondary efficacy variable for the trial is mortality prior to hospital discharge with unassisted breathing. Patients alive in hospital at day 60 will be considered to have survived.

- 2. Mortality before hospital discharge home, with unassisted breathing, to day 90. Patients alive in hospital to day 90 will considered to have survived
- 3. Number of ICU-free days at 28 days after randomization
- 4. Number of organ failure-free days at 28 days after randomization. Organ failure will be defined by previously validated definitions for renal, circulation, central nervous system, hematologic, and hepatic organ and system failures (Bernard, 1997).

Organ failure is defined as present on any date when the most abnormal vital signs or clinically available lab value meets the definition of clinically significant organ failure according to the Brussels Organ Failure Table. Patients will be followed for development of organ failures to death, hospital discharge or study day 28, whichever comes first. Each day a patient is alive and free of a given clinically significant organ failure will be scored as a failure-free day. Any day that a patient is alive and free of all 5 organ failures will represent days alive and free of all organ failure. Central nervous system dysfunction is evaluated using the Glasgow Coma Scale.

- 5. Number of days between the day of first meeting criteria for weaning-readiness (see Appendix G, section G.2.) and day 28 after randomization.
- 6. Mortality and VFDs in patients with pre-randomization $PaO_2/F_1O_2 \le 200$.
- 7. Change in plasma levels of IL-6, IL-8, VWF, SPD, and total protein concentrations from baseline to study day 3.
- 8. Ventilator free days and mortality prior to hospital discharge with unassisted breathing to day 60 and number of ventilator-free days to day 28 in patients with shock (defined in 2.1.2) at the time of randomization.

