6.6 Endpoint Determinations

- 1. Vital status at 28, 60, and 90 days until discharged home on UAB.
- 2. Time of initiation of unassisted breathing (assuming patient achieves 48 consecutive hours of unassisted breathing)
- 3. Need for re-instituting assisted or mechanical ventilation after achieving 48 consecutive hours of unassisted breathing
- 4. Status 48 hours after initiation of unassisted breathing
- 5. Date of ICU discharge
- 6. Date of Hospital discharge

7 Statistical Considerations

Primary Endpoint

The primary endpoint will be ventilator free days. All analyses will be intent to treat. A three-way analysis of variance will be used with factors shown in Table 1. The primary model will be a main effects model. The primary comparisons will be whether initial trophic feeding followed by full-calorie enteral feeding is different than initial advancement to full-calorie enteral feeding.

Table 1: Factorial Design

Factor	Level
	1. Omega-3 Fatty Acid, Gamma-linolenic acid (GLA), and anti-
Nutriceutical (Medical Food)	oxidant supplementation
	2. Placebo
	3. None
Time of Feeding	1. Initial trophic feeding followed by full-calorie enteral feeding
Time of Feeding	2. Initial advancement to full-calorie enteral feeding
Shock at baseline	1. Yes
Shock at baseline	2. No

The maximum sample size will be 1000 patients. The study will be monitored using a flexible group sequential design that stops for efficacy/futility. Since trophic vs. full-calorie feeding is a two-sided question with either strategy possibly improving outcomes, efficacy and futility stopping rules will be the same (i.e. efficacy of one strategy would be the same as futility of the other strategy). The reported confidence intervals on the treatment difference will be adjusted for the group sequential design using the method of Jennison & Turnbull.

In order to allow flexibility we will use alpha and beta spending boundaries as described by DeMets and Ware (zl=2.277,delta=1.663,zu=2.025,m=4, mu=3.3837) (DeMets, 1982). Trophic vs. full-calorie feeding is a two sided question which will have a two-sided efficacy boundary and an inner wedge futility boundary that will be formed by reflecting the lower futility boundary about the abscissa. There would be no chance of futility stopping of two sided factors at the first look.

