In this method of interim monitoring we specify a function a(t) and b(t) called the alpha and beta spending functions. The function a(t) gives the amount of the p-value that will be "spent" by a given time "t" in the study, where time runs from 0 at study start to 1 when all patients have been entered. It is the probability under the null hypothesis that the trial will stop for efficacy at or before time t. The function b(t) is the type II error that will be "spent" by the interim monitoring plan to allow futility stopping. It is the probability under the alternative hypothesis that the study will stop for futility at or before time t or that, at the last look, the efficacy boundary will not be exceeded. The reason that we use alpha and beta "spending" functions rather than p-values to stop the trial is that with two co-enrolled trials we may not be monitoring the data of both trials at 250 patient intervals.

Table 2 shows the alpha-spending boundary a(t) where t is the proportion of patients accrued at that DSMB meeting. In the table we have assumed 5 meetings at t= .10, .25, .50, .75 and 1.0 This function a(t) will be extended to a smooth function of t using a cubic spline as suggested by (Pampallona, 1994) and at each DSMB meeting the actual stopping boundary will be calculated so that the probability of stopping at or before that meeting is a(t). Similarly the futility boundary is defined by the beta-spending function b(t). The number b(t) is the cumulative probability that the results would be below the futility stopping boundary given the alternative hypothesis of a 2.25 day increase in VFD with a standard deviation of 10.5. At each DSMB meeting a futility stopping boundary will be calculated so that the probability of futility stopping at or before that meeting is b(t) at this alternative hypothesis.

The overall one-sided significance level of the study will be 0.025 which is equivalent to a two sided p=0.05 significance level. Five analyses are planned after 100, 250, 500, 750, and 1000 patients. Under the assumption that there are five equally spaced interim analyses the power of the study will be 90.7%. Changes in the number or spacing of the interim analyses will have a minor effect on the power. With this design, assuming that the pattern of deaths and extubations is similar to the FACTT fluid study, there is a 82% chance that the study will show both a significant effect of VFD and a nominally positive benefit in mortality.

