Mortality will be compared at interim data analyses using Kaplan Meier estimates at 60 days and their associated standard errors. This analysis will be stratified as above and a test for interaction of treatment with strata will be presented. At the end of the study sixty-day mortality will be compared using a Mantel-Haenzel test as long as all patients can be followed. If not the method used for the interim analyses will be used.

Other Endpoints

The number of ICU-free days, Organ-Failure Free days, and days from first weaning readiness will be analyzed in the same manner as is described above for the primary endpoint. In addition we will test for interactions between treatment and gender and race as per NIH guidelines (National Institutes of Health, 2001).

Changes in plasma levels of IL-6, IL-8, and protein will be compared in two analyses. An analysis of covariance will test for a treatment effect on the day 3 value of these variables using the day 0 value as a covariate. In addition, a multivariate analysis of variance will test for a baseline difference between day 3 and day 0.

Table 3 illustrates the detectable differences for endpoints, assuming 1000 patients enrolled, 90% power, and a two-sided alpha-level of 0.05.

Table 3: Detectable Differences for Secondary Endpoints

Variable	Incidence or Mean	Standard Deviation	Detectable Difference
PaO ₂ / FiO ₂	155	73	15
ICU free days	13.4 days	12.6 days	2.6 days
Shock free days	19.1 days	4.93 days	2.23 days
Plasma IL-6 (pg/ml)	1252	862	177
Plasma IL-8 (pg/ml)	149	93	19
28 day hospital mortality	22%		8.2%
90 day hospital mortality	25.4%		8.6%

Changes in physiologic lung indices on days 1-7 will be compared using a multivariate analysis of variance.

Twice during the early part of the study, the DSMB will evaluate the glucose control between the trophic and full-calorie arms to ensure that the levels of blood glucose are not clinically different between the groups over the first 6 days of the study. These evaluations will occur after approximately 100 and 250 patients are enrolled in the study. Should the blood glucose values differ between the groups at these evaluations, the guidelines for controlling blood glucose levels for the remainder of the study may be adjusted in an attempt to equalize the blood glucose levels for the study.

8 Data Collection and Site Monitoring

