- 12. There are no requirements for maintaining a specific PEEP to FiO₂ ratio. The lower PEEP / higher FiO₂ table represents a consensus approach developed by ARDS Network investigators in 1995. The higher PEEP / lower FiO₂ table (ALVEOLI) yielded equivalent results in a randomized trial (Brower, 2004) and would be acceptable and perhaps preferable in patients who appear to respond with substantial increase in arterial oxygenation in the transition from lower to higher PEEP.

Lower ELV/Higher FiO₂ Treatment Group

L.O	20	40	40	70	70	(0	70	70	70	0.0	00	00	00	1.0
FiO ₂	.30	.40	.40	.50	.50	.60	.70	.70	.70	.80	.90	.90	.90	1.0
PEEP	5	5	8	8	10	10	10	12	14	14	14	16	18	18-24

Higher ELV/Lower FiO₂ Study Group

					0					 				
FiO ₂	.30	.30	.30	.30	.30	.40	.40	.50	.50	.5080	.80	.90	1.0	1.0
PEEP	5	8	10	12	14	14	16	16	18	20	22	22	22	24

(Levels of PEEP in these FiO₂ / PEEP scales represent levels set on the ventilator, not levels of total-PEEP, auto-PEEP, or intrinsic-PEEP.)

- 13. No specific rules for respiratory rate, but incremental increase in the RR to maximum set rate of 35 if pH < 7.30.
- 14. No specific rules about I:E. Recommend that duration of Inspiration be ≤ duration of Expiration.
- 15. Bicarbonate is allowed (neither encouraged nor discouraged) if pH < 7.30.

Changes in more than one ventilator setting driven by measurements of PaO₂, pH, and Pplat may be performed simultaneously, if necessary.

G.2 Weaning

G.2.1 Commencement of Weaning

Patients will be assessed for the following weaning readiness criteria each day between 0600 and 1000. If a patient procedure, test, or other extenuating circumstance prevents assessment for these criteria between 0600 and 1000, then the assessment and initiation of subsequent weaning procedures may be delayed for up to six hours.

- (a) At least 12 hours since enrollment in the trial.
- (b) $FiO_2 \le 0.40$ and $PEEP \le 8$ cm H_2O or $FiO_2 \le 0.50$ and PEEP = 5 cm H_2O
- (c) Values of both PEEP and $FiO_2 \le values$ from previous day (comparing Reference Measurement values, section 6.3).
- (d) Not receiving neuromuscular blocking agents and without neuromuscular blockade

- (e) Patient exhibiting inspiratory efforts. If no efforts are evident at baseline, ventilator set rate will be decreased to 50 % of baseline level for up to 5 minutes to detect inspiratory efforts.

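### Secondary endpoint 5 (days from first weaning-readiness to day 28) leaves deaths after readiness unpenalized and gives no score to patients who never become ready

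*Protocol*

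**What the plan says.** Protocol section 3.2, item 5, counts the "Number of days between the day of first meeting criteria for weaning-readiness" and day 28. Nothing further is said about survival, extubation or patients who are never ready.

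The event that starts the count is defined in Appendix G.2.1: "Patients will be assessed for the following weaning readiness criteria each day between 0600 and 1000". The criteria concern time since enrollment, oxygen and PEEP settings, neuromuscular blockade, inspiratory effort and blood pressure. None depends on what happens to the patient afterwards.

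Two neighbouring endpoints do deal with death. For VFD, section 3.1 says: "If a patient was receiving assisted breathing at day 27 or dies prior to day 28, VFD will be zero". For organ failure, section 3.2, item 4, says: "Each day a patient is alive and free of a given clinically significant organ failure will be scored as a failure-free day".

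Section 7, under Other Endpoints, says that "days from first weaning readiness will be analyzed in the same manner as is described above for the primary endpoint".

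**The concern.** Item 5 is a complete formula: 28 minus the day of first readiness. Applied literally, a death on the day after readiness costs the patient nothing. The endpoint then cannot register an excess of deaths that follow readiness, although VFD and organ-failure-free days would register the same deaths.

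The protocol itself cares about this. When section 3.1 discusses a day count that ignores death, it remarks: "This example of decreased days of assisted ventilation is misleading as the treatment group actually had a worse outcome". Item 5 lacks the safeguard that section 3.1 builds into VFD.

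The missing value for never-ready patients is a second gap. Scoring them zero and leaving them out give different results, and the text does not choose. At stake is whether one listed secondary endpoint can be read alongside the primary endpoint without misleading anyone.

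**Working it through.** **What the plan gives.** There is no figure for item 5 to reproduce: Table 3 has no row for it, so no mean, standard deviation or detectable difference is stated. The stated power of 90.7% belongs to VFD ("alternative hypothesis of a 2.25 day increase in VFD with a standard deviation of 10.5") and plays no part below.

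**Inputs.**
- 28-day hospital mortality 22%, detectable difference 8.2 points (Table 3), so 22% versus 30.2%.
- Day of first readiness, and the share of deaths that come after it: not in the protocol. Assumed here: readiness on day 4-8, and 10-50% of the extra deaths after readiness. For the arm comparison: reference-arm readiness on day 8, with 20-60% of that arm's deaths after readiness.

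**Single patients.** The literal score is 28 − r, where r is the day of first readiness.
- Ready on day 3, dead on day 5: 28 − 3 = 25. With zero for death: 0.
- Ready on day 10, survives: 28 − 10 = 18 under either rule.

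**Omitted penalty at arm level.** Relative to a zero-for-death score, the amount that goes uncounted is 0.082 × share after readiness × (28 − r).
- Low end: 0.082 × 0.10 × (28 − 8) = 0.16 days.
- High end: 0.082 × 0.50 × (28 − 4) = 0.98 days.
- All extra deaths after readiness on day 8: 0.082 × 1 × 20 = 1.64 days.

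**Difference between arms (harmful minus reference), all extra deaths after readiness, never-ready patients scored 0.** Let p be the proportion dying before readiness, the same in both arms: from 0.22 × 0.8 = 0.176 down to 0.22 × 0.4 = 0.088. The literal mean is (1 − p)(28 − r). The zero-for-death mean is (1 − mortality)(28 − r).

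| Readiness day, reference / harmful | Literal | Zero for death |
|---|---|---|
| 8 / 8 | 0.00 | 0.698 × 20 − 0.78 × 20 = −1.64 |
| 8 / 7 | +0.82 to +0.91 | 0.698 × 21 − 0.78 × 20 = −0.94 |
| 8 / 6 | +1.65 to +1.82 | 0.698 × 22 − 0.78 × 20 = −0.24 |

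With equal readiness days the literal score shows no difference: the excess deaths neither help nor hurt. If the harmful arm is ready earlier by more than 0 and less than 0.78 × 20 / 0.698 − 20 = 2.35 days, the two rules point in opposite directions.

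**Never-ready patients.** Suppose instead that all the extra deaths come before readiness, with readiness otherwise on day 8. If these patients score zero, the harmful arm loses 0.082 × 20 = 1.64 days. If they are left out, the difference is 0.00. It would turn in the harmful arm's favour only if the patients lost were ones who would otherwise have become ready late.

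**Does section 7 import the VFD death rule?** The primary-endpoint text it points back to gives intention to treat, the model ("A three-way analysis of variance will be used with factors shown in Table 1") and the monitoring boundaries. The zero for death stands in section 3.1 and is not repeated there.

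**The case against.** The strongest reply is that death cannot bring first readiness forward. Section 3.1 warns of a different mechanism, in which death shortens time on the ventilator and so improves the count. A reader might infer from item 5 that extra deaths earn an arm extra days. The text does not support that: the 8 / 8 row is 0.00, and 0.16-0.98 is a penalty left out, not a gain between arms. If the harmful arm does become ready earlier, item 5 is reporting a real fact about readiness.

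Moreover, if only 10-50% of the extra deaths follow readiness, then 50-90% precede it. Scored zero, these count against the harmful arm, by 0.082 × 0.5 × 20 = 0.82 to 0.082 × 0.9 × 20 = 1.48 days with readiness on day 8. This stands, but only if never-ready patients do score zero, which item 5 does not say.

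The cross-reference in section 7 might be read as carrying over the VFD death rule, and an analysis plan not seen here might say so. That reading is possible. But the sentence concerns analysis, the text it refers to contains no scoring rule, and item 5 as fixed would still say otherwise.

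Two further inferences are tempting and should not be drawn:
- *That ICU-free days (item 3) is wrong in the same way.* Item 3 names the endpoint without a scoring rule, a detail commonly left to an analysis plan. Table 3's mean of 13.4 ICU-free days lies below the assumed mean of 14 VFD, which already scores death as zero. This suggests, without proving, that deaths are penalized there too.
- *That the count should restart when readiness is lost.* Item 5 deliberately uses first readiness. Counting from the last continuous period would be another endpoint, and Appendix E schedules ventilator parameters only on days 0-4, 6, 12, 21 and 28.

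**Conclusion.** The point holds in a limited form. As written, item 5 ignores deaths after first readiness and leaves never-ready patients without a score, out of line with VFD and organ-failure-free days. For an 8.2-point mortality excess the omitted penalty is about 0.16-0.98 days under the assumed range, and 1.64 days if every extra death follows readiness on day 8. For scale only, Table 3's detectable differences for shock-free and ICU-free days are 2.23 and 2.6 days; item 5 has none of its own.

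The timing of readiness and the share of deaths after it are assumptions, so the sizes are illustrative. That such deaths go uncounted follows from the definition alone. A misleading advantage for the harmful arm needs something more: earlier readiness in that arm, or exclusion of never-ready patients who would have been ready late.

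The consequence is confined to one of eight secondary items. The primary endpoint and its boundaries are untouched, mortality is reported in items 1 and 2, and section 7 advises the monitoring board to weigh mortality differences.

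**What to change.** Add one sentence to section 3.2, item 5: *Patients who die before day 28, or who do not meet the criteria by day 28, score zero.* Keep first readiness as the start of the count.

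The cost is one sentence. Vital status at day 28 is already collected (section 6.6 and Appendix E), and the day of first readiness is needed for item 5 in any case, so no new data are required. The model in section 7 need not change.

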3.3 Other Endpoints

Many of these proposed outcomes are not meant to definitively establish the underlying mechanisms, but instead will explore biochemical endpoints to provide additional support or generate other hypotheses of how the interventions may result in different clinical outcomes.

- 1. Increase of PaO₂ / FiO₂ ratio on study days 1-7
- 2. Improvement in Lung Injury Score on study days 1-7
- 3. Number of gastrointestinal intolerances (aspiration, vomiting, regurgitation, diarrhea, elevated gastric residual volumes, abdominal distention and cramping) on study days 1-7
- 4. Level of systemic inflammation, as measured by plasma IL-6 and IL-8 levels.

5.

- 6. Measure of oxidative stress on days 3, 6 and 12 compared to baseline as measured by urinary levels of F₂-isoprostane metabolites
- 7. Incidence of bacteremia.
- 8. Incidence of Clostridium dificile induced diarrhea.
- 9. Incidence of ventilator-associated pneumonia
- 10. Serum levels of markers of nutrition, including albumin and total protein levels between baseline and days 6 and 12.

Clostridium dificile diarrhea will be diagnosed by one or more daily stool specimen positive for cytotoxin assay or enzyme immunoassay. Patients with more than 3 liquid stools totaling more than an estimated 500 ml of stool per day, or those with systemic inflammatory response

syndrome unexplained by other infection, may have up to three daily stool samples sent for *C. difficile* investigation (either cytotoxin assay or enzyme immunoassay).

Bacteremia will only be considered if it develops greater than 24 hours after the initiation of study procedures and is documented with a positive blood culture. The primary medical team, using clinical judgment, will determine when blood cultures are sent. Coagulase negative (or thermo nuclease negative) *Staphylococci* or *Corynebacterium* bacteremia require the isolation of these organisms from at least two blood cultures drawn within 24 hours of each other containing the same organism in order to be deemed significant.

Ventilator-associated pneumonia (VAP) is a difficult diagnosis to make with certainty, especially in patients with underlying ALI or ARDS. However, for the purposes of this trial, an objective definition of VAP will be used in order to standardize the reporting and reduce bias during the first 6 days of enteral feeding given the unblinded administration of enteral feeding volumes. As such, VAP will be defined using the same scoring system as the ARDS network used for the LaSRS study (Calandra, 2005). The scoring system incorporates temperature, leukocyte count, sputum or tracheal aspirate Gram stain and culture, and chest radiograph results. This score will be calculated as available as long as the patient remains ventilated. The certainty of VAP will be graded as either suspected or possible vs. probable using the criteria listed in Appendix A.

4 Study Population and Enrollment

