5.1.3.1 Trophic Enteral Feeding Treatment Group (Trophic Feeding Group)

All patients randomized to trophic enteral feedings will have enteral feeds started at 20 kcal / hr and continued at this rate for 144 hours (see Trophic Feeding Protocol, Appendix C) provided gastric residuals remain at an acceptable level (see Gastric Residuals, section 5.1.4) and provided the patient remains on the ventilator. Thus, patients in the trophic feeding arm will receive 480 kcal, which is approximately 25% of total caloric goals each day. This caloric delivery lies within the range of data from published studies in animals and neonatal humans (Burrin, 2000; McClure, 2000; Ohta, 2003; Omura, 2000; Owens, 2002; Tyson, 2005). After 144 hours of trophic enteral feeds, the feeding rate will be advanced to full-calorie rates using the same protocol as for the full-calorie feeding treatment group (see section 5.1.3.2 and Appendix D) provided the patient remains on the ventilator.

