6.3 Assessments During Study

The following data will provide the basis for assessing protocol compliance and safety as well as between-group differences in several efficacy variables. Data for each of the variables will be recorded on the days shown in the Time-Events schedule (Appendix E) or until death, discharge from the intensive care unit, or unassisted ventilation for 48 hours.

Reference Measurements

The following parameters will be measured and recorded between 4:00 and 10:00 A.M. using the values closest to 8:00 A.M. on the days specified in the Time-Events schedule (Appendix E). The following conditions will be ensured prior to measurements: no endobronchial suctioning

for 10 minutes; no invasive procedures or ventilator changes for 30 minutes. All vascular pressures will be zero-referenced to the mid-axillary line.

- 1. If receiving positive pressure ventilation:
 - (a) Ventilator mode
 - (b) PEEP level
 - (c) Total minute ventilation
 - (d) Tidal Volume
 - (e) Plateau airway pressures
- 2. FiO₂
- 3. PaO₂, PaCO₂, pH, and SpO₂
- 4. Hemodynamic values
 - (a) Systemic arterial systolic, diastolic and mean blood pressures
 - (b) Heart Rate (beats/min)

Values for the following variables will be recorded for the dates shown in the Time-Events Schedule (Appendix E). If the measurements are not obtained during the 6-hour reference interval (4:00 to 10:00 A.M.), then the value obtained closest in time to the reference interval on the respective date will be recorded. If more than one value is obtained during the reference interval, then the value obtained closest to 8:00 A.M. will be recorded.

- 5. Blood hemoglobin concentration, white blood cell count, prothrombin time (PT), and platelet count.
- 6. Serum electrolytes, creatinine, and glucose
- 7. Units of insulin at time of daily glucose value (infusion) or total insulin in the 6 hours prior to the glucose value (subcutaneous)
- 8. Serum total protein, albumin, magnesium, phosphorus
- 9. Requirements for the following medications (Y / N):
 - (a) Sedatives and narcotics
 - (b) Neuromuscular blocking agents
 - (c) Vasopressors
 - (d) Pro-kinetic agents (e.g. metoclopramide, erythromycin, lactulose, or sorbitol)
 - (e) Laxatives and fiber products
 - (f) Anti-diarrheal agents
 - (g) Methylprednisolone equivalents greater than 20 mg
- 10. Frontal Chest Radiograph Lung Injury Score
- 11. Brussels Score data (Bernard, 1997)
 - (a) Worst PaO₂ / FiO₂ ratio for the date.

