Serum magnesium and phosphorus	Х	Х	Α	Х	Α	Α	Α	Α	Х	Α	Α	Α	Α				
Total Protein and Albumin	Х	Х	Α	Α	Α	Α	Α	Х	Α	Α	Α	Α	Х				
Ventilator–Associated Pneumonia assessment ^v	Α	Α	Α	Α	Α	Α	Α	Α	Α	Α	Α	Α	Α	Α	Α	Α	
Insulin dose at time of glucose level	Α	Α	Α	Α	Α	Α	Α	Α	Α	Α	Α	Α	Α				
Location of Feeding tube (e.g., gastric, post-pyloric) *	Х	Α	Α	Α	Α	Α	Α	Α	Α	Α	Α	Α	Α				
Volume of tube feeds / Calories delivered *		Х	Х	Х	Х	Х	Х	Х	Х	Х	Х	Х	Х				
Number and type of Gastrointestinal Intolerances		Х	Х	Х	Х	Х	Х	Х	Х	Х	Х	Х	Х				
Pro-kinetic agents, anti-diarrheals, anti-emetics * (Y/N)	Х	Х	Х	Х	Х	Х	Х	Х	Х	Х	Х	Х	Х				
Prothrombin Time	Α	Α	Α	Α	Α	Α	Α	Α	Α	Α	Α	Α	Α				
Plasma for Cytokines IL-6 and IL-8	Х			Х			Х						Х				
Urine isoprostane metabolites	Х			Х			Х										
Whole blood for DNA	Х																
Episode of bacteremia (record positive blood cultures) *		Α	Α	Α	Α	Α	Α	Α	Α	Α	Α	Α	Α	Α			
Clostridium dificile diarrhea tests		Α	Α	Α	Α	Α	Α	Α	Α	Α	Α	Α	Α	Α			
Vital Status §																Х	Х

A=When available

 $^{^{\}text{C}}=$ Labs not available in the 24 hours before randomization must be obtained

V = VAP assessment from available CXR, sputum culture, gram stain and WBC until extubated or day 28, whichever occurs first *= Data gathered at times indicated or until 48 hours UAB, whichever occurs first **=On day 28 or hospital discharge dates.

B=Records clinically available creatinine, platelets, bilirubin, SBP and vasopressor use

^{~=}Data gathered on days 0-28 or until d/c from study hospital

^{#=}Measure during reference period (0600-1000); other values may be obtained closest to 0800 on the specified calendar date §=Measure at 90 days and 12 months as part of Long Term outcome.

F Adverse Events

1. Procedures for Reporting Adverse Events

Assuring patient safety is an essential component of this protocol. Each participating investigator has primary responsibility for the safety of the individual participants under his or her care. The Principal Investigator will evaluate all adverse events. The Study Coordinator must view patient records for possible adverse events throughout the study period. All adverse events occurring within the study period must be reported in the participants' case report forms.

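### The exploratory albumin and total protein endpoint is set at days 6 and 12, but Appendix E requires the tests on days 7 and 12, so its day 6 comparison rests on clinically ordered values

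*Protocol*

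**What the plan says.** Section 3.3 (Other Endpoints), item 10, lists "Serum levels of markers of nutrition, including albumin and total protein levels between baseline and days 6 and 12". The follow-up days are thus 6 and 12.

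Appendix E (Time-Events Schedule) has one row for these tests, "Total Protein and Albumin". It carries an X on days 0, 1, 7 and 12 and an A on every other day up to day 12, including day 6. The footnote reads "A=When available".

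Section 6.3 makes the schedule govern collection: data are "recorded on the days shown in the Time-Events schedule (Appendix E"), or until death, ICU discharge or 48 hours of unassisted ventilation. It lists "Serum total protein, albumin, magnesium, phosphorus" without naming separate days. If nothing was measured in the morning reference interval, "then the value obtained closest in time to the reference interval on the respective date will be recorded".

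Two further statements bear on the choice of day. Section 5.1.3.1 says "After 144 hours of trophic enteral feeds, the feeding rate will be advanced to full-calorie rates". Section 3.3, in explaining the pneumonia definition, refers to the "unblinded administration of enteral feeding volumes".

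**The concern.** The endpoint and the schedule disagree on the first follow-up day. Followed as written, the protocol obtains a required sample on day 7 that no listed endpoint uses, and has no required sample on day 6, which the endpoint does use.

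Two things are at stake for the day 6 comparison. The first is precision, because only patients whose clinicians happened to order the test contribute. The second is selection, because staff know the feeding arm and the decision to order could depend on it. Section 9.3 names lower protein intake over the first six days, with possible catabolism, as a risk of trophic feeding. The early nutrition marker is therefore of some interest, even though it is exploratory.

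**Working it through.** **Is the mismatch an artefact of the table?** The Appendix E header has 17 day columns: 0 to 12, then 14, 21, 28 and 60. The row has 13 entries followed by 4 blanks, and 13 + 4 = 17, so it is not shifted.

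| Day | 0 | 1 | 2 | 3 | 4 | 5 | 6 | 7 | 8 | 9 | 10 | 11 | 12 |
|---|---|---|---|---|---|---|---|---|---|---|---|---|---|
| Total protein, albumin | X | X | A | A | A | A | A | X | A | A | A | A | X |

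Against the endpoint: baseline is required, day 6 is not, day 12 is.

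**Does other text repair it?**
- The substitution rule in section 6.3 works only within the same calendar date, so a day 7 result cannot stand in for day 6.
- The research plasma required on day 6 is frozen for inflammatory markers. Nothing says that it supplies serum albumin or total protein.
- The other protein endpoint (section 3.2, item 7) concerns plasma at day 3, so it does not use the day 7 serum draw either.

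**How far is day 7 from the end of the feeding contrast?** Inputs: feeds start within 6 hours of randomization (section 5.1.3), the trophic period lasts 144 hours (section 5.1.3.1), and reference values are those closest to 8:00 A.M. (section 6.3). Assumptions: day 0 is the calendar day of randomization, and feeding is uninterrupted.
- Earliest end: start at 00:00 on day 0, plus 144 h = 00:00 on day 6.
- Latest end: randomized at the close of day 0, start at 06:00 on day 1, plus 144 h = 06:00 on day 7.
- 08:00 on day 7 is therefore 2 h (from 06:00 on day 7) to 32 h (24 + 8, from 00:00 on day 6) after the period ends.
- 08:00 on day 6 ranges from 8 h after the end to 22 h before it.

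**Precision.** The protocol gives no day 6 ordering rate and no detectable difference for this endpoint, so there is no stated figure to reproduce. If a proportion p of patients in each arm is tested, the standard error relative to complete sampling is 1/√p:
- p = 0.7: 1/√0.7 = 1.20
- p = 0.4: 1/√0.4 = 1.58

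The range 0.4 to 0.7 is an assumption. The comparator is idealised, because required draws also stop at death, ICU discharge or 48 hours of unassisted ventilation.

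**The case against.** The strongest reply is that little depends on this. Item 10 is the last of the other endpoints, many of which section 3.3 describes as exploratory and hypothesis-generating. Section 7 attaches no named test, alpha or stopping rule to albumin. That is right, and it fixes the weight of the point.

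Three stronger readings are tempting, and the protocol does not support them.
- A reader might infer that the whole endpoint rests on clinically selected values. It does not: baseline and day 12 are required draws.
- A reader might infer that the day 6 comparison is biased. Ordering that varies only with site (a randomization stratum) or with baseline illness (balanced in expectation) changes who is measured, but does not by itself distort the contrast between arms. Bias needs ordering, or its dependence on illness after randomization, to differ by arm. Unblinded feeding makes that possible, and nothing shows that it happens.
- A reader might infer that day 7 comes too late to be useful. In the full-calorie protocol (section 5.1.3.2), which the trophic arm then follows, the rate rises by 25 cc/hr every 6 hours. A morning value 2-32 hours after the trophic period can still reflect mostly the six days of contrast. A day 6 morning value can itself come up to 22 hours before the period ends.

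It may also be said that an analysis plan could settle the day. It could choose day 7, but it cannot recover day 6 samples that were never drawn.

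**Conclusion.** The inconsistency is real and confined to the first follow-up day of an exploratory endpoint. As written, the day 6 comparison uses only values that clinicians ordered, and a required day 7 value has no stated use. The cost is lost precision, with a standard error about 1.2 to 1.6 times larger if 40-70% are tested (an assumption, against idealised complete sampling), and a possible but unquantified selection by arm. The timing figures rest on day 0 being the calendar day of randomization and on uninterrupted feeding. Correcting this is desirable but not critical.

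**What to change.** Reconcile section 3.3, item 10, with the Appendix E row.

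**Preferred:** define the endpoint as the change from baseline to days 7 and 12. This alters one number in the text, adds no draws and uses samples already required for all patients. The downside is that the day 7 value may fall roughly 2-32 hours after the trophic period ends, which is worth a sentence in the protocol.

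**Alternative:** make day 6 the required draw for future patients and day 7 the optional one. The number of required draws stays the same, but this is more than a table edit. Section 4.1 says the first 272 patients were enrolled during the factorial phase. If they followed the same schedule (not stated), early patients would have a required day 7 value and later ones a required day 6 value. The protocol would then have to say how patients enrolled under the day 7 schedule are handled.

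If day 6 is kept as it stands, report the number tested in each arm and describe that comparison as based on clinically ordered values.
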